4.2.2.1. Prescribed Adherence

The level of prescribed adherence to each type of the study will be determined by the total amount of study drug administered relative to the total amount of study drug specified by the protocol for a subject who completes treatment in the study.

The level of prescribed adherence will be expressed as a percentage using the following formula:

$$\text{Prescribed Adherence (\%)} = \left(\frac{\text{Total Amount of Study Drug Administered}}{\text{Total Amount of Study Drug Specified by Protocol}} \right) \times 100$$

Note: If calculated adherence is greater than 100%, the result will be set to 100%.

Descriptive statistics for the level of prescribed adherence with the number and percentage of subjects belonging to adherence categories (< 75%, ≥ 75 to < 90%, and $\geq 90\%$) will be provided for each study drug by treatment group for the Safety Analysis Set.

No formal statistical testing is planned.

By-subject listings of study drug administration and drug accountability will be provided separately by subject ID number (in ascending order) and visit (in chronological order).

4.3. Protocol Deviations

Subjects who did not meet the eligibility criteria for study entry, but enrolled in the study will be summarized regardless of whether they were exempted by the medical monitor or not. The summary will present the number and percentage of subjects who did not meet at least 1 eligibility criterion and the number of subjects who did not meet specific criteria by treatment group based on the All Randomized Analysis Set. A by-subject listing will be provided for those subjects who did not meet at least 1 eligibility (inclusion or exclusion) criterion. The listing will present the eligibility criterion (or criteria if more than 1 deviation) that subjects did not meet and related comments, if collected.

Protocol deviations occurring after subjects entered the study are documented during routine monitoring. The number and percentage of subjects with important protocol deviations by deviation reason (e.g., nonadherence to study drug, violation of select inclusion/exclusion criteria) will be summarized by treatment group for the All Randomized Analysis Set. A by-subject listing will be provided for those subjects with important protocol deviation.

5. BASELINE CHARACTERISTICS

5.1. Demographics

Subject demographic variables (ie, age, sex, race, and ethnicity) will be summarized by treatment group and overall using descriptive statistics for age, and using number and percentage of subjects for sex, race, and ethnicity. Age is calculated in years at the date of first study drug administration. The summary of demographic data will be provided for the Safety Analysis Set.

A by-subject demographic listing, including the informed consent date, will be provided by subject ID number in ascending order.

5.2. Other Baseline Characteristics

Other baseline characteristics include:

- body weight (in kg)
- height (in cm)
- body mass index as a continuous variable and as categories ($< 18.5 \text{ kg/m}^2$, $18.5 \text{ to } < 25 \text{ kg/m}^2$, $25 \text{ to } < 30 \text{ kg/m}^2$, and $\geq 30 \text{ kg/m}^2$)
- diabetes mellitus (diabetic or nondiabetic)
- MRI-PDFF
- MRE
- FibroScan (if available)
- FibroSURE/FibroTest
- ELF test
- ALP
- ALT
- AST
- direct and total bilirubin
- GGT

- estimated glomerular filtration rate (eGFR) (Cockcroft-Gault)
- homeostasis model assessment of insulin resistance (HOMA-IR)
- fasting glucose
- fasting insulin
- international normalized ratio (INR)
- hemoglobin A1c (HbA1c)
- total cholesterol
- triglycerides
- high-density lipoprotein cholesterol (HDL-C)
- calculated low-density lipoprotein cholesterol (LDL-C)
- calculated Non-HDL-C
- calculated Very Low Density Lipoprotein cholesterol (VLDL-C)
- free fatty acid
- C-reactive protein (CRP)
- Total bile acids
- waist circumference
- systolic blood pressure treated status (treated/not treated)
- smoking status

These baseline characteristics will be summarized by treatment group and overall using descriptive statistics (n, mean, SD, median, Q1, Q3, minimum, and maximum) for continuous variables and using number and percentage of subjects for categorical variables. The summary of baseline characteristics will be provided for the Safety Analysis Set. No formal statistical testing is planned.

[figure not shown]
A by-subject listing of then Other Baseline Characteristics will be provided by subject ID number in ascending order.

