#### Chemistry:

Alanine aminotransferase (ALT), aspartate aminotransferase (AST), albumin, alkaline phosphatase (ALP), bicarbonate, blood urea nitrogen (BUN), calcium, chloride, creatinine, glucose, lactate dehydrogenase (LDH), magnesium, phosphorus, potassium, sodium, total and direct bilirubin, total protein, uric acid, gamma-glutamyl transferase (GGT). Also includes C-Peptide and Insulin for the Baseline/Day1, Week 4, and 12 visits.

Creatinine clearance is calculated by the Cockcroft-Gault equation {Cockcroft 1976} using actual body weight (BW). The calculation will be performed by the central laboratory.

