3.8.2. Definition Analysis Visit Windows

Subject visits might not occur on protocol-specified days. Therefore, for the purpose of analysis, observations will be assigned to analysis windows.

In general, the baseline value will be the last nonmissing value on or prior to the first dosing date of study drug. For imaging the data, baseline will be the first nonmissing value from screening up to first dosing date plus 4 weeks.

Selected safety and efficacy data collected up to and including the last dosing date plus 30 days (or 42 days for imaging data) will be mapped according to the following analysis windows. Early termination (ET) or follow-up (FU) will use the nominal visit name.

Table 3-1. Analysis Visit Windows for Vital Signs Including Weight, Chemistry, Hematology, Coagulation Labs, Lipid Profile, and Pooled Cohort Score and Risk

Analysis Visit	Study Day	Lower Limit	Upper Limit
Baseline/Day	1	NA	1
Week 1	8	2	18
Week 4	29	19	42
Week 8	57	43	70
Week 12	85	71	> 85

NA = not applicable

Table 3-2. Analysis Visit Windows for FibroSure/FibroTest, CK-18, ELF (and its components), Free Fatty Acid, C-Reactive Protein, ApoA1, ApoB, and Bile Acids

Analysis Visit	Study Day	Lower Limit	Upper Limit
Baseline/Day	1	NA	1
Week 1	8	2	18
Week 4	29	19	56
Week 12	85	57	> 85

Table 3-3. Analysis Visit Windows for Insulin and HOMA-IR

Analysis Visit	Study Day	Lower Limit	Upper Limit
Baseline/Day	1	NA	1
Week 4	29	2	56
Week 12	85	57	> 85

Table 3-4. Analysis Visit Windows for Waist Circumference, ECG, HbA1c, and QoL-Questionnaire

Analysis Visit	Study Day	Lower Limit	Upper Limit
Baseline/Day	1	NA	1
Week 12	85	2	> 85

Table 3-5. Analysis Visit Windows for FibroScan, MRE, and MRI-PDFF

Analysis Visit	Study Day	Lower Limit	Upper Limit
Baseline/Day	1	NA	29
Week 12	85	30	> 85

Data relating to unscheduled visits may be assigned to a particular visit or time point. The following conventions will be followed:

- An unscheduled visit prior to the first dosing of study drug will be included in the calculation of the baseline value.
- For subjects who prematurely discontinue from the study, early termination (ET) data will be summarized as a separate visit, labeled as “Early Termination Visit”
- Data collected on a follow-up visit will be summarized as a separate visit, and labeled “Follow-up Visit.”

3.8.3. Selection of Data in the Event of Multiple Records in an Analysis Visit Window

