- AEs leading to premature discontinuation of study drug
- AEs leading to premature discontinuation of study
- AEs leading to temporary interruption of study drug

7.2. **Laboratory Evaluations**

Laboratory data collected during the study will be analyzed and summarized using both quantitative and qualitative methods. The analysis will be based on values reported in conventional units. When values are below the LOQ, they will be listed as such, and the closest imputed value will be used for the purpose of calculating summary statistics as specified in Section 3.7.

A by-subject listing for laboratory test results will be provided by subject ID number and visit in chronological order for hematology, serum chemistry, and urinalysis separately. Values falling outside of the relevant reference range and/or having a severity grade of 1 or higher according to the CTCAE, Version 4.03 will be flagged in the data listings, as appropriate.

No formal statistical testing is planned.

7.2.1. **Summaries of Numeric Laboratory Results**

Descriptive statistics will be provided by treatment group for each laboratory test listed below:

- Chemistry Panel:
Creatinine, fasting glucose, fasting insulin, eGFR using the Cockcroft-Gault equation, serum creatinine
- Coagulation Panel: INR
- Hematology: white blood cell (WBC), neutrophils, lymphocytes, hemoglobin, platelets

For each laboratory test specified above, the descriptive statistics will be provided as follows:

- Baseline values
- Values at each postbaseline visit
- Change from baseline at each postbaseline visit

Change from baseline to a postbaseline visit will be defined as the postbaseline value minus the baseline value. The mean, median, Q1, Q3, minimum, and maximum values will be displayed to the reported number of digits; SD values will be displayed to the reported number of digits plus 1.

Median (Q1, Q3) of the observed values for albumin, creatinine, glucose, fasting insulin, WBC, neutrophils, lymphocytes, hemoglobin, platelets, INR, and eGFR will be plotted using a line plot by treatment group and visit.

In the case of multiple values in an analysis window, data will be selected for analysis as described in Section 3.8.3.

7.2.2. **Graded Laboratory Values**

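### The visible SAP summarises HOMA-IR and fasting insulin without separating insulin-treated subjects, so injected insulin can pass as insulin resistance and can distort arm means and SDs

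*SAP*

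**What the plan says.** **Who can enrol.** Protocol 5.1 stratifies randomization by diabetes, and use of diabetes medication is one way to qualify as diabetic. No exclusion criterion in Protocol 4.3 names diabetes or insulin. Neither the list in Protocol 5.4 nor Table 5-1 names insulin.

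**What is summarised.** SAP 5.2 includes "homeostasis model assessment of insulin resistance (HOMA-IR") and fasting insulin, and states: "The summary of baseline characteristics will be provided for the Safety Analysis Set". Continuous variables are reported "using descriptive statistics (n, mean, SD, median, Q1, Q3, minimum, and maximum) for continuous variables". SAP 3.8.2 supplies "Table 3-3. Analysis Visit Windows for Insulin and HOMA-IR", at Baseline, Week 4 and Week 12. The chemistry panel in SAP 7.2.1 reads "Creatinine, fasting glucose, fasting insulin, eGFR using the Cockcroft-Gault equation, serum creatinine", with values and change from baseline by visit.

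**What handling is visible.** SAP 3.6.2 keeps all data and plans no sensitivity analysis for outliers. SAP 3.7 allows transformation or nonparametric methods in general terms. SAP 7.2.1 plots fasting insulin as median and quartiles. The diabetes subgroup analysis in SAP 6.3 covers MRE and MRI-PDFF only.

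**What else is collected.** Protocol 6.8.1, Chemistry, says: "Also includes C-Peptide and Insulin for the Baseline/Day1, Week 4, and 12 visits". C-peptide appears in no visible SAP summary.

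**The concern.** HOMA-IR is normally computed from fasting insulin and fasting glucose, and it is read as an index of resistance because the insulin is taken to be the subject's own. In a subject who injects insulin, an assay that detects the injected product returns a value that partly follows dose and timing. Protocol 6.8.1 requires fasting and has study drug taken after the visit, but no visible text deals with the timing of injected insulin.

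Two things are at stake. The first is meaning: an insulin user's HOMA-IR does not measure what its label says, whichever summary statistic is used. The second is leverage: a few high values in a small arm can move its mean and SD. Protocol 1.3.1 says that effects on carbohydrate metabolism, insulin included, will be closely monitored, so a reader will look at these tables.

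**Working it through.** The documents state no figure for insulin use, insulin level or HOMA-IR, so there is no plan figure to reproduce. What follows is an illustration over a range.

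**Inputs from the documents.** Placebo n = 25 and each active arm n = 50 (SAP 1.2.1).

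**Assumptions.** *k* insulin users per arm. Users' values average *r* times the mean of the other subjects, with *r* = 2, 5 or 10. The assay detects injected insulin. HOMA-IR is the usual product of fasting insulin and fasting glucose, scaled by a constant.

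**Step 1: arm mean.** Inflation = ((n − k) + k·r)/n. Users' share of the arm total = k·r/((n − k) + k·r).

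For 3 users of 25:
- r = 2: (22 + 6)/25 = 1.12; share 6/28 = 21%
- r = 5: (22 + 15)/25 = 1.48; share 15/37 = 41%
- r = 10: (22 + 30)/25 = 2.08; share 30/52 = 58%

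Other cases (mean inflation at r = 2 / 5 / 10):

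| Users | n = 25 | n = 50 |
|---|---|---|
| 1 | 1.04 / 1.16 / 1.36 | 1.02 / 1.08 / 1.18 |
| 3 | 1.12 / 1.48 / 2.08 | 1.06 / 1.24 / 1.54 |
| 5 | 1.20 / 1.80 / 2.80 | 1.10 / 1.40 / 1.90 |

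**Step 2: apparent difference between arms.** With 3 users in placebo and 3 in an active arm, and no true difference, the ratio of placebo mean to active mean is 1.12/1.06 = 1.06, 1.48/1.24 = 1.19 or 2.08/1.54 = 1.35.

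**Step 3: SD.** Mixing users and non-users adds a between-group SD of √(p(1 − p))·(r − 1), in units of the other subjects' mean, with p = k/n. For 3 of 25, p = 0.12 and √(0.12 × 0.88) = 0.325. The added component is therefore 0.325, 1.30 or 2.92 times the other subjects' mean at r = 2, 5 or 10. It combines with the within-group spread as a sum of squares.

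**Step 4: median.** Simulation with a lognormal distribution (log-SD 0.6 assumed, 4,000 runs):
- 3 of 25 at r = 5: mean ×1.48, median ×1.11
- 3 of 25 at r = 10: mean ×2.09, median ×1.11
- 5 of 50 at r = 10: mean ×1.90, median ×1.09

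**Step 5: how many users supply more than half of an arm's total?** 9, 5 or 3 of 25, and 17, 9 or 5 of 50, at r = 2, 5 or 10.

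**Step 6: chance imbalance.** Ignoring stratification, if 6 of 125 subjects used insulin (assumed), placebo would expect 6 × 25/125 = 1.2 users and would have none with probability 25%. With 15 of 125 it would expect 3, and would have none or one with probability 15%.

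**The case against.** Several points on the other side have force.

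- **Robust statistics are already planned.** Medians and quartiles stand beside the means, and the fasting-insulin plot uses them. This stands against the leverage argument. It does not answer the argument about meaning: a median over users and non-users still mixes two quantities.
- **Change from baseline.** A user on a stable dose carries a high level at both visits, and much of it subtracts out. The calculation above concerns levels only, so it says nothing direct about a drug-effect comparison. A dose change during the trial would not subtract out, but its frequency is unknown.
- **Redaction.** The exploratory endpoints and models (Protocol 8.1.3, SAP 6.1 and 6.2.1) are blacked out. A HOMA-IR formula or a rule for insulin users may be there. The tables in SAP 5.2 and 7.2.1 are visible, and they have none.
- **Partial handling.** Stratification limits imbalance in diabetes, the pool from which insulin users come, but not in insulin use itself. SAP 7.4.2 tabulates concomitant medications by arm, so insulin use will be visible, though not linked to these tables. Protocol 8.6.3 promises summaries of selected laboratory data only, so leaving C-peptide unsummarised breaches nothing.
- **Limited reach.** All of this is descriptive or exploratory, with no formal testing.

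A reader might infer that a few insulin users will dominate the arm means or decide the HOMA-IR comparison. The documents do not support that. They give neither the number of users nor the size of their values; one user of 25 at twice the others' mean moves the arm mean by only 4%; and the comparison itself lies in redacted text.

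**Conclusion.** The point holds as a gap in the visible SAP. Insulin-treated subjects can enrol, and HOMA-IR at baseline and fasting insulin at baseline and by visit are summarised for everyone with no separation by insulin use. Where the assay detects injected insulin, those subjects' values do not measure resistance.

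The numerical effect is possible but not established. With 3 users of 25 it runs from a 12% to a 108% rise in the placebo mean across the assumed 2-fold to 10-fold ratios. The simulated median rises by about 11% at the 5-fold and 10-fold ratios. These figures rest on an assumed number of users, an assumed ratio, the usual HOMA-IR formula and an assay that detects injected insulin. The primary safety objective and the MRI-PDFF responder analysis are untouched.

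**What to change.** In the SAP:

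1. Define baseline insulin use from the concomitant-medication data: insulin started before, and continuing at, the first dose.
2. Restrict HOMA-IR summaries, at baseline and for change, to subjects not using insulin at baseline. Give the number of baseline users by arm.
3. Keep the all-subject fasting-insulin table in 7.2.1 and add a split by baseline insulin use. Removing users from it would conflict with Protocol 8.6, which has all safety data in the treatment and 30-day follow-up period summarised by treatment group.
4. Flag, and do not drop, subjects who start insulin or change its dose after baseline. Dropping subjects who are on insulin at a given visit would condition on a post-randomization event that treatment may influence, and could remove subjects unequally by arm.
5. Summarise C-peptide, to which injected insulin does not contribute, for all subjects at Baseline, Week 4 and Week 12.
6. If the redacted sections already contain such a rule, cross-refer to it from 5.2 and 7.2.1.

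The cost is SAP wording and programming, with no new sample or visit. Protocol 9.1.5 requires concomitant-medication dates and dose changes in source; whether the eCRF holds dose should be confirmed for step 4. The downside is slightly fewer subjects in the HOMA-IR table.

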5.3. Medical History

General medical history data will be collected at screening and listed only. General medical history data will not be coded.

6. EFFICACY ANALYSES

6.1. Exploratory Efficacy Endpoints

CCI

6.1.1.

CCI

- [REDACTED]
- [REDACTED] ■ [REDACTED]
- [REDACTED]

[REDACTED]

[REDACTED]

6.2. Analysis Methods for Exploratory Efficacy Endpoints

6.2.1. Statistical Analysis Models

CCI

[REDACTED]

CCI

6.2.2. Statistical Analysis Methods

For exploratory efficacy endpoints, the number and percentage of subjects in each category will be presented for categorical variables. Descriptive statistics (n, mean, SD, median, Q1, Q3, minimum, and maximum) will be provided for continuous exploratory efficacy variables by treatment group, as follows:

- Baseline values
- Values at each postbaseline visit
- Change from baseline at each postbaseline visit
- Percent change from baseline at each postbaseline (except for pooled cohort risk score)

Change from baseline at a postbaseline visit will be defined as the visit value minus the baseline value. Percent change from baseline will be defined as (the visit value – the baseline value)/the baseline value $\times 100\%$. The mean, median, Q1, Q3, minimum, and maximum will be displayed to the same reported number of digits, and SD will be reported to the number of digits plus 1.

For continuous exploratory efficacy endpoints, mean (SD) of the observed change from baseline values will be plotted using a line plot by treatment group and visit.

Listings of all exploratory efficacy endpoints will be provided.

6.2.3. Missing MRI-PDFF Data Handling

For MRI-PDFF data, the first analyzable value from multiple echo (ME) series at each time point will be used. The mean of all analyzable segments by time point reported will be used. If there are subjects missing ME series results but have double double echo (DDE) series results, 95% CI based on t statistics will be calculated for the mean difference in ME and DDE series results. If the 95% CI is within $[-3\%, 3\%]$, then the DDE values (mean of analyzable segments reported) will be used to impute for missing ME results. If a subject has both (baseline and Week 12) DDE series values available, and at least 1 ME series value requires imputation, then the corresponding DDE series result will be used for both visits.

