biochemistry (e.g. ALT and GGT); noninvasive serum markers of liver injury (e.g. serum CK-18, FibroTest® and ELF™ Test); and imaging-based methods for quantifying hepatic steatosis (MRI-PDFF) and fibrosis (MRE and FibroScan®). An important endpoint of interest is the proportion of subjects achieving  $\geq 30\%$  reduction in steatosis as assessed by MRI-PDFF. This level of reduction has been associated with a significant improvement in NASH histology ( $\geq 2$ -point reduction in NAFLD Activity Score) {Patel 2015}. Based on preclinical and clinical data, a treatment duration of 12 weeks with GS-0976 is expected to be sufficient to lead to meaningful improvements in hepatic steatosis on MRI-PDFF and liver biochemistry. Liver histology has not been included as an endpoint because it is not feasible to repeat this invasive procedure over a 12-week study. In addition to these liver-related endpoints, the effects of GS-0976 on carbohydrate and lipid metabolism (e.g. with glucose, insulin, free fatty acids, apolipoproteins, lipid profiles, and metabolites) will be closely monitored in light of the mechanism of action of GS-0976 and the importance of metabolic dysfunction in contributing to the morbidity and mortality (e.g. cardiovascular) of subjects with NASH.

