### **6.2. Pretreatment Assessments**

#### **6.2.1. Screening Visit**

Subjects will be screened within 6 weeks prior to randomization to determine eligibility for participation in the study. The Screening period may be extended under special circumstances with the explicit approval of the Gilead Medical Monitor.

Subjects who previously failed screening in GS-US-426-3989 can be re-screened in the following situations:

- Previously screen failed due to a low MRE or MRI-PDFF measurement, but have an MRE  $\geq 2.5$  kPa and MRI-PDFF  $\geq 8\%$  within 6 months of prior Screening/Re-screening.
- Previously screen failed due to a low MRE or MRI-PDFF measurement and have a historical liver biopsy within 12 months of Screening/Re-screening that is consistent with NASH (defined as the presence of steatosis, hepatocellular ballooning, and lobular inflammation) with fibrosis, but not cirrhosis.
- Previously screen failed due to a FibroSURE/FibroTest®  $\geq 0.75$  in whom Gilbert's syndrome or hemolysis is present; a repeat FibroSURE/FibroTest® calculated using direct bilirubin instead of total bilirubin will be used to determine eligibility.

- Previously screen failed due to a FibroSURE/FibroTest®  $\geq 0.75$  and with a historical liver biopsy within 12 months of Screening that does not reveal cirrhosis; FibroSure/Fibrotest score will not be used to determine eligibility.

If MRE and MRI-PDFF were performed within 6 months of re-screening, MRE and MRI-PDFF does not need to be repeated. If prior imaging was performed greater than 6 months prior to re-screening, MRE and MRI-PDFF must be repeated. A historical MRE and MRI-PDFF within 6 months of screening in another Gilead study (i.e. GS-US-384-3914, GS-US-402-1852) may be used to determine eligibility into this study. All other screening procedures must be repeated and meet eligibility criteria.

Screening labs may be repeated within the Screening period, prior to administration of study drugs to rule out laboratory error, if any. This will be done at the discretion of the investigator.

Subjects should be instructed to fast (no food or drink, except water), starting from midnight (00:00) or earlier, as appropriate, on the evening prior to the Screening visit to ensure an approximate 8-hour fast prior to the fasted blood sample collection the next morning.

The following will be performed and documented at Screening:

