1.3. Sample Size and Power

Due to the exploratory nature of this study, no formal power calculations were used to determine sample size. The number of subjects was chosen based on clinical experience with other similar proof-of-concept studies. However, assuming that 4% of subjects in the Placebo arm (N = 25) and 32% in the GS-0976 20 mg arm (N = 50) have a \geq 30% reduction in MRI-PDFF at Week 12, this sample size will provide 80% power to detect the difference between GS-0976 and Placebo based on a 2-sided Fisher's exact test at a significance level of 0.05.

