6.3. Subgroup Analysis of the Efficacy Endpoints

Subgrouping of subjects based on randomization stratification factors will be explored as follows:

- presence of diabetes mellitus
- absence of diabetes mellitus

Descriptive statistics for the above subgroups will be presented for the baseline values, values at each postbaseline visit, change from baseline, and percent change from baseline by visit for MRE and MRI-PDFF.

For each subgroup, the proportion of subjects with at least 30% reduction in MRI-PDFF at Week 12 and the proportion of subjects with at least 15% reduction in MRE at Week 12 will be reported for each treatment group by using a point estimate and 95% CI of the proportion

based on the Clopper-Pearson method. The 95% CI for the difference in proportion between GS-0976 and Placebo will also be provided.

Within each subgroup, the change from baseline of MRI-PDFF and MRE at Week 12 will be analyzed by using an ANCOVA model, with treatment group, and baseline MRI-PDFF or MRE as covariates. For change from baseline, LS means and 95% CIs of LS means will be reported for each treatment group. For treatment differences (GS-0976 – Placebo) of changes from baseline of MRI-PDFF or MRE at Week 12, LS means and 95% CIs will be reported.

Mean (SD) of the observed change from baseline value will be plotted using a line plot by treatment group and visit for subjects from each subgroup.

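### Does SAP 6.2.3 need another rule for subjects whose MRI-PDFF comes from one echo series at baseline and the other at Week 12?

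*SAP*

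**What the plan says.** SAP 6.2.3 sets out a sequence of rules for MRI-PDFF.

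- **Default.** "the first analyzable value from multiple echo (ME) series at each time point will be used".
- **Gate.** Where ME is missing and DDE exists, a "95% CI based on t statistics will be calculated for the mean difference in ME and DDE series results". The margin is -3% to 3%.
- **General rule.** If the interval lies inside the margin, "then the DDE values (mean of analyzable segments reported) will be used to impute for missing ME results".
- **Same-sequence rule.** "If a subject has both (baseline and Week 12) DDE series values available, and at least 1 ME series value requires imputation", DDE is used at both visits.

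SAP 3.6.1 points to 6.2.3 for the handling of missing MRI-PDFF. The section is not redacted.

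The outcomes affected are the change in MRI-PDFF and "the proportion of subjects with at least 30% reduction in MRI-PDFF at Week 12" (SAP 6.3). Protocol 1.3.1 gives the responder outcome some weight: "An important endpoint of interest is the proportion of subjects achieving" a fall of at least 30%. It is also the only outcome with a stated power (SAP 1.3): "this sample size will provide 80% power to detect the difference between GS-0976 and Placebo". Protocol 8.5 and SAP 3.5 both say that no formal statistical comparison will be made.

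**The concern.** The same-sequence rule shows that the authors preferred not to mix sequences within a subject. It needs DDE at both visits, so it misses a subject with ME only at one visit and DDE only at the other. That subject falls to the general rule, and any ME-DDE offset enters the change score directly. It could create a 30% response where nothing changed, or hide a real one.

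The gate limits the average offset, not agreement in individuals, while a responder call is made subject by subject. The text also leaves two things unsaid: whether 3% means fat-fraction points or relative percent, and which ME-DDE pairs enter the interval. With 25 placebo subjects, one wrong call moves the placebo rate by 4 points.

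A possible source of mixed pairs is the allowance in Protocol 6.2.1: "A historical MRE and MRI-PDFF within 6 months of screening in another Gilead study" may be used for eligibility, and the documents do not say which series such scans contain.

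**Working it through.** **Inputs from the documents:** 25 placebo and 50 subjects on 20 mg, response rates of 4% and 32%, two-sided Fisher test at 0.05 (SAP 1.3); entry MRI-PDFF of at least 8% by the imaging route (Protocol 4.2); gate of ±3% (SAP 6.2.3).

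**Assumptions, because the documents give no figure:** the ME-DDE offset, its SD, the number of pairs and the share of mixed subjects. The margin is read as fat-fraction points, the reading under which the problem is larger.

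**1. The plan's own figure.** Exact enumeration over Binomial(25, 0.04) and Binomial(50, 0.32), with Fisher's test at 0.025 per tail, gives 80.3% power, in line with the stated 80%. Summing all tables no more probable than the observed one gives 85.0%. The power statement is not in dispute.

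**2. What the gate lets through.** Largest passing observed mean = 3 - t(0.975, n-1) × SD/√n.

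| SD (points) | n = 50 | n = 100 |
|---|---|---|
| 1.5 | 2.57 | 2.70 |
| 3 | 2.15 | 2.40 |

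At n = 50 and SD 1.5: 3 - 2.010 × 1.5/7.071 = 2.57. At zero mean difference and n = 50, the gate still passes with an SD up to 3 × 7.071/2.010 = 10.6 points. It does not test individual agreement.

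**3. Probability of a false response in one mixed subject.** With ME at baseline b, DDE at Week 12, no true change and DDE low by d points, the probability is Φ((d - 0.30b)/SD). With SD 1.5:

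| Baseline | Threshold 0.30b | d = 0 | d = 1 | d = 2 |
|---|---|---|---|---|
| 8% | 2.4 | 5.5% | 17.5% | 39.5% |
| 10% | 3.0 | 2.3% | 9.1% | 25.2% |
| 15% | 4.5 | 0.1% | 1.0% | 4.8% |
| 20% | 6.0 | <0.1% | <0.1% | 0.4% |

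In the other direction, with DDE high by d at Week 12, a true 40% fall reads below 30% with probability 1 - Φ((0.10b - d)/1.5). For d = 1 this is 55% at baseline 8% and 37% at 15%, against 30% and 16% for d = 0.

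If the margin is relative, a 3% offset makes an unchanged subject read -3% and a true 30% fall read 0.70 × 1.03 - 1 = -27.9%.

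**4. From one subject to the arm.** The figures in step 3 apply only to a subject who is already mixed. Assume 5% of placebo subjects are mixed, all in the ME-then-DDE order and none truly changed: 0.05 × 25 = 1.25 subjects. Expected false placebo responders are 1.25 times the probability in step 3.

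| Baseline | d = 1 | d = 2 |
|---|---|---|
| 8% | 0.22 | 0.49 |
| 10% | 0.11 | 0.32 |
| 15% | 0.01 | 0.06 |

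**5. One whole false responder, in placebo only.** 1/25 against 16/50 gives Fisher p = 0.007; 2/25 against 16/50 gives p = 0.024. The difference falls from 28 to 24 points.

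**6. Cost of setting mixed pairs to missing.** If 5% of subjects are lost (24 against 48), power by the 0.025-per-tail method is 77.5%. At 10% lost (22 against 45) it is 73.0%.

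**The case for a change.** The strongest case for a change is that the plan discards a usable ME value to keep one sequence per subject, so leaving some mixed pairs with no flag, count or sensitivity analysis is inconsistent. A gate on the mean cannot protect a responder call, and with a 2-point offset a mixed subject at the 8% entry limit has about a 40% chance of a false response. A few lines of text would deal with it, and would cost nothing if no such subject exists.

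The reading and the arithmetic stand. Four points reduce what follows from them.

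- The case is not undefined. The general sentence gives it an answer: use the DDE value once the gate has passed.
- The group needs ME unusable at one visit and DDE unusable at the other in the same subject. SAP 6.2.4 lets an analyzable repeat scan replace the original, which may reduce missing ME. The outside-study route is uncertain. Protocol 6.2.1 admits such scans for eligibility, whereas SAP 3.8.2 takes the imaging baseline as the first value from screening onwards.
- The calculation gives same-sequence subjects no visit-to-visit error. Ordinary repeat-scan noise would also misclassify some of them, so step 3 overstates the excess due to mixing.
- Excluding mixed pairs is not clearly better. It loses subjects and leaves open whether they leave the responder denominator or count as non-responders.

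The missing details can be filled sensibly. MRI-PDFF is itself reported in percent and the gate concerns a difference of results, so points is the natural unit. SAP 6.2.2 uses the term percent change when it means a relative quantity. The number of pairs matters little: going from 50 to 100 moves the largest passing mean from 2.57 to 2.70 at SD 1.5.

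**Conclusion.** No change to the plan follows. SAP 6.2.3 does allow a mixed-sequence change score for a narrow group, and its gate does not test individual agreement. What remains is unstated detail that an analyst can settle, plus a fair trade-off between a gated DDE value and no value.

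The likely effect is small. With 5% of placebo subjects mixed and none truly changed, a 2-point offset and an SD of 1.5, about 0.3 false placebo responders are expected at baseline 10% and 0.06 at 15%. The figure rises to about 0.5 only if all of them sit at the 8% entry limit. Even one whole false responder, placed in placebo alone, leaves a 24-point difference, and the p-value has no decision role.

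This rests on assumed values for the offset, SD and share of mixed subjects. A much larger mixed group, concentrated at low baselines, would weaken it. The endpoint definitions and main models in SAP 6.1 and 6.2.1 are redacted, so a relevant convention there cannot be excluded. If mixed pairs do occur, their number by arm and a rerun without them can be reported without altering the planned analysis.
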